Active Powered Prosthesis (APEX) for Spinal Cord Injury

Protocol #6100003-100 Rev A

Study Sponsor: AbiliTech Medical Inc. & The National Institutes of Health (R43HD094440)

Principal Investigator:	[name], MS, OT/L Program Coordinator for Spinal Cord Injury Program and Research Clinician, Courage Kenny Rehabilitation Institute
Clinical Supervisor:	[name], DO Medical Director, Spinal Cord Injury Rehabilitation, Courage Kenny Rehabilitation Institute
Co-Investigator:	[name], OTR/L Occupational Therapist, Instructor Scientist, Assistive Technology Supervisor
Engineering Director:	[name], MS VP R&D, AbiliTech Medical
Abilitech Clinical Director:	[name]. Clinical and Product Manager, AbiliTech Medical
Design Req Specialist:	[name], BS CEO and President, AbiliTech Medical
Technical Specialist:	[name]. Lead Software Engineer, AbiliTech Medical
Research Project Manager:	[name], BS Project Manager, AbiliTech Medical

Courage Kenny Rehabilitation Institute
Allina Health
[name]
[name]

Protocol Synopsis

Introduction

The Active Powered Prosthesis (APEX) (AbiliTech Medical Inc., Minneapolis, MN) is a proof-of-concept shoulder-elbow-wrist prosthesis device intended to provide non-invasive active powered robotic assistive movement to the upper extremities. In September 2017, the National Institutes of Health approved and funded the development of the APEX device through a Phase I SBIR Grant.

(1R43HD094440-01). The APEX device is designed for users with upper level cervical spinal cord injuries and motor impairment of their upper extremities. AbiliTech Medical has a history of developing upper extremity prosthesis devices. The AbiliTech Assist device is an upper limb passive powered lift and assist device planned for release in Q3 2018. The APEX device represents an advancement from the AbiliTech Assist device by providing active power sources to lift and rotate the upper limbs. The increased range of motion provided by the APEX device will expand the activities of daily living (ADL's) for users of the APEX device.

Study Objectives

Objectives:

Perform focus groups with subjects and clinicians to evaluate a proof of concept active powered prosthesis.

1. Perform a focus group with three to six individuals with chronic tetraplegia to evaluate the user control interface of an active powered prosthesis device proof-of-concept prototype. Subjects will provide feedback on the device function and usability after manipulating the device on a mannequin.
2. Perform a focus group with Courage Kenny Research Institute Clinicians to validate device safety features, performance and assess the potential clinical utility of the device.

Primary Outcomes:

The following will be assessed:

1. User ability to control APEX device to manipulate objects in space
2. User ability to control APEX to move an object in a preferred pathway
3. User ability to control APEX device to push buttons
4. User ability to control APEX to lift a phone
5. Evaluate subject reported outcomes within their interaction with the APEX device through interviews and a survey

Secondary Outcomes:

1. To observe and assess any uncontrolled device guided movement during the APEX device testing on mannequin
2. Gain clinician feedback on device safety control mechanisms

Ancillary Data:

1. Subject Acclimatization/ Learning Time to Operate the APEX Device
2. Characterization of focus group population:
 - a. Medical History: Diagnosis, level of injury, AIS classification; MMT Scores (shoulder, elbow, forearm, hand)
3. Feedback on device design
4. Feedback on user input control system

Study Design/Subject population

The study design will be that of a single arm pilot testing study with three to six study subjects (n=3-6).

Target user population will be human subjects with spinal cord injury at levels C3 to C5, and ASIA

Impairment Scale (AIS) A, B, or C. Inclusion and exclusion criteria are summarized below:

3.1 Inclusion Criteria:

1. Spinal cord injury at levels C3 to C5, and AIS A, B, or C
2. Greater than 3-months post injury or surgery to spinal column, arms, or shoulder
3. Ability to provide informed consent
4. Age 18 or over
5. Selected for participation based on investigator discretion

3.2 Exclusion Criteria:

1. Unable to follow instructions
2. Exhibit significant behavioral problems or impaired cognitive ability
3. Inability to provide consent
4. Non-English speaker

Clinicians involved in overseeing the device manipulation portion of the study will be expected to provide feedback about the APEX device.

Recruitment Process:

After IRB approval, subjects with upper extremity spinal cord injuries will be recruited through:

1. An internal search of subject records within Courage Kenny Rehabilitation Institution performed by an out-patient care coordinator.
2. This pilot study will be posted and listed on www.clinicaltrials.gov with contact information available for possible enrollment in the study. Due to the size (n=3-6) of this study and recruitment methods, issues with recruitment of subjects is not anticipated.

In-Clinic Evaluation

There are two components to this study:

1. Visit 1: User Focus Group:
 - a. Consent/Subject Evaluation
 - b. Study participant Body Measurements
 - c. Device Testing
 - d. Focus Group Discussion and Feedback
2. Visit 2: Clinical Focus Group:
 - a. Presentation of Results
 - b. Clinical Discussion

The duration of time between visits 1 and 2 is expected to be 2-4 weeks. User focus group participants will receive a \$50 Visa gift card after completion of all study activities.

Evaluation of Outcomes

Primary and secondary outcome measurements will be recorded during the study to assess and validate the device feasibility for function and safety. Data will be collected and reported without statistical analysis. This study is designed to assess early feasibility and prepare for a larger clinical study in the

future. Primary functional and safety outcomes will be compiled and reviewed to assess the performance of the APEX device in meeting the requirements of SCI subjects. Pilot Study results and conclusions on performance will be provided by AbiliTech Medical and Allina investigators.

Table of Contents

1. Introduction	6
2. Objectives	9
3. Trial Population	9
4. Study Design.....	10
5. Evaluations.....	12
6. Outcomes	13
7. Criteria for Study Discontinuation	13
8. Statistical Considerations.....	13
9. Retention of Records	13
10. Amendments to the Protocol	14
11. Deviations from Investigative Plan	14
12. Informed Consent Process.....	14
14. Risk to Participants	15
15. References.....	15
Appendix 1: Medical History Report Form.....	18
Appendix 2: Pilot Usability Testing Form	18
Appendix 3: AbiliTech Medical APEX Device Feedback Questions	20
Appendix 4: AbiliTech Medical APEX Device Feedback Questions	23
Appendix 5: AbiliTech Medical APEX Device Clinician Feedback Questions	36

1. Introduction

1.1. Disease Background

Spinal cord injuries (SCI) cause costly and morbid chronic conditions such as lack of voluntary movement, increased chance of pressure sores, problematic spasticity, loss of bowel, bladder, and sexual function, and more physical impairments which result in a lower quality of life and lack of independence. Approximately 285,000 people in the U.S. have SCI with approximately 17,000 new subjects added each year [1]. It is recognized that 54% of SCI's are cervical injuries resulting in upper extremity neuromuscular motor impairment [2]. Through a published survey, 48.7% of quadriplegics indicated that regaining arm and hand function would be the preferred treatment to improve quality of life [3,4].

While there are no treatments that reverse all morbidities of SCI, cellular research, spinal cord stimulation, and advanced high-intensity fitness regimens show promise in treating the effects of SCI and improving independence and quality of life [5,6,7]. Remarkably, subjects with AIS A or B injuries, defined as “complete” motor and sensory loss and “incomplete” with sensory but not motor function, respectively, have shown improvement in motor scores after 6 months with structured exercise (20). Moreover, advances in independence have been shown in subjects with complete injuries after year-long rehabilitation programs (22). These, and studies on orthotics and exoskeletons used to improve strength and neuromuscular health have focused mainly on the lower extremity (1-4) and restoration of lower extremity function on improving independence in activities of daily living (ADLs) in subjects with cervical SCI (6).

Recent advances in upper extremity orthotics with devices such as a mobile arm support, WREX, Armeo Robotic Arm Trainer, MyoPro, and the Swedish arm support have led to strengthened upper extremities and improved independence in activities of daily living (ADLs) of those with cervical SCI [14,15,16]. They are limited by cost, size, comfort, weight, and functionality [14]. Another important limitation is that many of these devices focus on in-clinic rehabilitation and limit the frequency of rehab opportunities and insurance coverage. Recent studies have shown a significant correlation between high frequency of rehab sessions and improved outcomes [7,17,18].

1.2. AbiliTech Medical APEX Background

The Active Powered Prosthesis (APEX) is a portable upper extremity prosthesis device that helps users with upper extremity motor impairment move their upper extremities through active robotic assistance. The device is controlled through body motion activation (i.e.: a body mounted 9 degree of freedom accelerometer sensor that is wirelessly connected to the device to interpret the user's movement into upper extremity assisted movement). The APEX device body chassis is worn by the user and has onboard processing, power, motors, sensors, and cables attached to the motors . Cables attached to the motors will extend throughout the body chassis to enable actuation of the user's upper extremities. The APEX is designed for optimal subject safety including mechanical, electrical and software stops to prevent uncontrolled device movement and injury to subjects.

Arm movement is activated and controlled by the APEX control system (ACS-III) consisting of body mounted movement control inputs and sensors, an on-board processor, sensors, motors, and firmware. While the APEX mechanical design is the initial concept model, the ACS III control system represents a third-generation control and data collection design. User directed control inputs will be

body motion activated, sensors will be placed on the head and/or combination of a head mounted joystick and buttons.

This is a first of its kind proof-of-concept model using a mobile Bowden-Cable robotic system to mobilize the upper extremity. A similar published research device called the CAREX [19] has demonstrated proof-of-concept but is stationary and has limited data on its use.

AbiliTech Medical has experience in developing similar devices. The AbiliTech Assist and the Hand Grip glove, funded by the State of Minnesota Spinal Cord and Traumatic Brain Injury Research Grant Program, are devices currently in development by AbiliTech Medical. The AbiliTech Assist is a hybrid power device. Motors power (active) the compression or relaxation of multiple arm and shoulder springs (passive) to provide lift and assist for users with reduced upper extremity mobility. The AbiliTech Hand Grip System, uses motors and cables to help users grasp and hold different objects and is similar in cable driven architecture to the APEX device. The APEX device will be a third-generation device leveraging the design architecture eg. ACS-III and clinical learning experience.

1.3. Other Similar Devices

To date, there are no mobile devices available that provide shoulder-elbow active motion assistance to individuals with upper extremity motor impairment. There are similar devices, such as the Hocoma Armeo® Power which assists with shoulder elbow and wrist movement and diagnosis and the MyoPro, which is mobile but only provides elbow and gripping assistance.

1.4. Study Rationale

Currently there are no effective mobile devices that enable people with limited upper extremity movement to move their upper extremities, especially for individuals with upper level SCI (C1-5). This

severely limits independence, reduces the ability for individuals with this condition to complete ADL's and makes them dependent on caregivers to complete all physical interactions with their environment. We hypothesize that the APEX device can safely enable and control shoulder-elbow movement to improve ADL performance and independence. Individuals with upper level cervical spinal cord injury that have lost functional use of their arms have a high potential to increase their quality of life by using this device which justifies observing their interaction with the APEX Focus Group.

2. Objectives

Objectives:

Perform focus groups with subjects and clinicians to evaluate a proof of concept active powered prosthesis.

1. Perform a focus group with three to six individuals with chronic tetraplegia to evaluate the user control interface of an active powered prosthesis device proof-of-concept prototype. Subjects will provide feedback on the device function and usability after manipulating the device on a mannequin.
2. Perform a focus group with Courage Kenny Research Institute Clinicians to validate device safety features, performance and assess the potential clinical utility of the device.

Primary Outcomes:

The following will be assessed:

1. User ability to control APEX device to manipulate objects in space
2. User ability to control APEX to move an object in a preferred pathway
3. User ability to control APEX device to push buttons
4. User ability to control APEX to lift a phone
5. Evaluate subject reported outcomes within their interaction with the APEX device through interviews and a survey

Secondary Outcomes:

1. To observe and assess any uncontrolled device guided movement during the APEX device testing on mannequin
2. Gain clinician feedback on device safety control mechanisms

Ancillary Data:

1. Subject Acclimatization/ Learning Time to Operate the APEX Device.
2. Characterization of focus group population
 - a. Medical History: Diagnosis, level of injury, AIS classification
 - b. Subject examination: MMT scores
3. Feedback on device design
4. Feedback on user input control system

3. Trial Population

Target user population will be three to six individuals with spinal cord injury at levels C3 to C5, and AIS A, B, or C. Inclusion and exclusion criteria are below:

3.1 Inclusion Criteria:

1. Spinal cord injury at levels C3 to C5, and AIS A, B, or C
2. Greater than 3-months post injury or surgery to spinal column, arms, or shoulder
3. Ability to provide informed consent
4. Age 18 or over
5. Selected for participation based on investigator discretion

3.2 Exclusion Criteria:

1. Unable to follow instructions
2. Exhibit significant behavioral problems or impaired cognitive ability
3. Inability to provide consent
4. Non-English speaker

Clinicians involved in overseeing the device manipulation portion of the study will be expected to provide feedback about the APEX device.

4. Study Design

Part 1: The study design will be that of a single-arm pilot study with three to six human subjects (n=3-6). The study will inform the AMI design team of customer and APEX design requirements needed to develop an APEX device for commercial release. Participants will be expected to attend one 180 minute session. AbiliTech Medical personnel will be present for user training, during all device evaluation sessions and to troubleshoot technical problems. Courage Kenny Rehabilitation Institute (CKRI) personnel will collect subject medical history from medical records once consent and HIPAA authorization are obtained. Appendix 1, section 1 includes subject information to be collected. Potential participants will receive the consent form ahead of time to read and study. At the start of visit 1, subjects will be consented as a group and sign the HIPPA authorization. During device testing, Appendix 2 and 3 include assessment forms for device testing and questions subjects will be asked. Appendix 4, includes the device feedback survey which will be completed onsite before conclusion of the study. Subjects will use their personal internet connected mobile device to access and complete the survey. If subjects do not have a mobile device, a tablet will be available for subject to use and complete the survey. Audio recordings will be taken and videos of the mannequin will be recorded during device movement. Table 1 highlights activities to be performed in the User Focus Group.

Table 1: Visit 1: User Focus Group Activities

	Activity	Description
1: Consent (Up to 30 minutes)	1.1: Review and Sign Informed Consent Form (0-30 minutes)	Study participants will review and sign consent form in a group setting. They will be given time as to review and provide consent. Consent forms will be mailed to scheduled participants in advance of the focus group session.
2: Device Testing and Follow up (approximately 90 minutes)	2.1: Device Instructions and Operational Testing (60 minutes)	The clinician and AbiliTech Personnel will describe to the user on how to operate the device. The study participant will acclimate to use of the device. Data will be collected on the operation, function, and performance of the APEX device. Safety risks will be assessed.

	2.2: Device & Follow Up (10-15 minutes)	The study participant will provide feedback about their experience with the device.
3: Device Feedback (approximately 30-60 minutes)	3.1 Complete Survey	Subject performs Survey Monkey Survey on Device Preferences. Compensation provided upon survey completion.

Part 2 of the study will comprise of a clinician focus group to evaluate data gathered in the user focus group, AbiliTech bench testing, and motion capture data of the device function. Appendix 5 includes questions for clinicians to answer. Table 2 highlights the Clinician focus group activities.

Table 2: Visit 2: Clinician Focus Group Activities

	Activity	Description
1: Data Review (approximately 60 minutes)	1.1: Study Data Presentation	AbiliTech Medical will present data to CKRI clinical team. Data includes User focus group results and results device bench testing.
2: Device Feedback (approximately 60 minutes)	2.1 Discussion on Device	Clinicians and AbiliTech Medical team members will discuss the safety and clinical utility of the APEX device.

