4.1 Test Schedule

Tests reflect common Activities of Daily Living, important safety measures, ancillary data, and subject satisfaction and interaction with the APEX Device crucial for successful development of the APEX Device.

Table 3: Test Schedule

Outcome Measure	Notes	Visit		
		After consent and HIPAA authorization obtained	1	2
Medical History	CKRI research staff will gather pertinent medical history of subjects ahead of clinical visit.	X		
Mannequin Test #1: Object Movement	Can the subject manipulate the device on a mannequin to manipulate an object in space? (Assistive Grip Device Allowed for use)? (Yes/No)		Assisted	
Mannequin Test #2: Object Movement	Can the subject manipulate the device on a mannequin to manipulate an object in a preferred pathway (Assistive Grip Device Allowed for use)? (Yes/No)		Assisted	

with Intention				
Mannequin Test #3: Button Push	Can the subject manipulate the device on a mannequin to push an elevator button? (Yes/No)		Assisted	
Mannequin Test #4: Lift Cell Phone	Can the subject manipulate the device on a mannequin to lift a cell phone? (Yes/No)		Assisted	
Safety: Observational Data on uncontrolled device guided movement	Observe if uncontrolled device movement occurs (Yes/No)		X	
Time using Device	Record time subject spends using device		X	
Open Ended Feedback	Data recorded from study participants from set questions. (See Appendix 2)		X	
Data Review				X
Clinician Feedback				X

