Appendix 5: AbiliTech Medical APEX Device Clinician Feedback Questions

[name]
[contact] www.abilitechmedical.com

AbiliTech Medical APEX Device Clinician Feedback Questions

APEX Study Questions

1. Are there features that should be integrated into the device to enhance clinical utility?

2. Do you have any safety concerns for the use of this device?

3. Do you have feedback on how safety mechanisms can be improved?

4. How would this device benefit your patients?

5. What motions or activities of daily living would be most meaningful for your patients?

6. What type and intensity of training and acclimation would you like to work with your patients for this device?

7. Are you interested in monitoring subject compliance with device?

8. What improvements of the device would you suggest?

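### Clinicians' views on the safety controls (secondary outcome 2) are scheduled only at Visit 2, after the sponsor's presentation, with no independent record beforehand

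*Combined protocol and SAP*

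**What the plan says.** Section 2 (repeated in the Synopsis) lists two secondary outcomes. The first is observation of uncontrolled device movement during mannequin testing. The second is "Gain clinician feedback on device safety control mechanisms".

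Section 3 says who is to give feedback, without saying when: "Clinicians involved in overseeing the device manipulation portion of the study will be expected to provide feedback about the APEX device".

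The timing comes from three places:

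- **Table 3 (Section 4.1).** The row "Clinician Feedback" is marked under Visit 2 only, directly below a data-review row that is also Visit 2 only.
- **Synopsis, In-Clinic Evaluation.** "The duration of time between visits 1 and 2 is expected to be 2-4 weeks".
- **Table 2 (Section 4).** The first activity is headed "1: Data Review (approximately 60 minutes)", and its description begins "AbiliTech Medical will present data to CKRI clinical team". The material shown is the user focus group results and bench testing. The second activity, also about 60 minutes, is the feedback: "Clinicians and AbiliTech Medical team members will discuss the safety and clinical utility of the APEX device".

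The clinician instrument is Appendix 5, which Section 4 introduces with Part 2. It has eight questions. Question 2 reads "2. Do you have any safety concerns for the use of this device", question 3 asks how the safety mechanisms could be better, and question 8 asks for device improvements. The plan does not say whether the questions are answered individually or as a group, in writing or aloud, or at what moment in Visit 2.

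**The concern.** Section 3 expects feedback from clinicians who watched the device being operated. That observation happens at Visit 1, but the only scheduled request for their opinion comes weeks later, after the developer has presented its results, and in a discussion the developer's staff join. If a clinician noticed something about the stops or controls at Visit 1, no planned step captures it as that clinician's own view before the group meets.

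The outcome carries weight in the plan. Objective 2 uses the clinician group to validate the safety features. Section 6 judges feasibility subjectively, names clinician feedback among its three components, and adds that investigator and clinician feedback on overall performance also counts. Section 8 rules out statistical analysis, so no numerical criterion stands beside these opinions. The sponsor presents the data, takes part in the discussion and shares in writing the conclusions. It plans a Phase II grant application if the pilot succeeds. The report should therefore let a reader see what clinicians thought independently and what emerged from the joint session.

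**Working it through.** No arithmetic applies: the plan gives no power, alpha or precision figure, and the question is one of order and timing. The check was to find every point at which clinicians' opinion on the safety controls could be recorded.

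**Visit 1, as scheduled**

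- Table 1, activity 2.1 says safety risks will be assessed, but names neither an assessor nor a form.
- Appendix 2 has a Yes/No item on uncontrolled movement with room to comment, and a notes field. That item serves secondary outcome 1. It records an event, not an opinion on the safety controls.
- Section 4 provides for audio recording and for video of the mannequin while the device moves. These may hold clinicians' remarks, but nothing prompts them.
- Table 1, activities 2.2 and 3.1, and the open-ended feedback row of Table 3 collect opinion from study participants, not clinicians.

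Scheduled requests for clinician opinion at Visit 1: none.

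**Between visits:** an expected 2-4 weeks, with no clinician form.

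**Visit 2, as scheduled**

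- Activity 1: sponsor presentation, about 60 minutes.
- Activity 2: feedback by discussion with sponsor staff, about 60 minutes.
- Appendix 5: answered at some unstated point.

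Scheduled requests for clinician opinion at Visit 2: one, listed second.

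**Comparison with the users.** Participants give feedback straight after testing (10-15 minutes, Table 1) and complete their survey before the same session ends. The clinicians, who are the source for a safety outcome, have no same-day record. Yet Section 14 places clinical staff beside the subjects throughout device use, so clinicians are present and could be asked.

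**How much of Appendix 5 is touched.** Questions 2, 3 and 8 are those on which direct observation at Visit 1 plausibly bears. Questions 4 to 7 (patient benefit, meaningful activities, training, compliance monitoring) do not depend on remembering that session. The issue therefore centres on three of the eight questions.

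**What is inferred.** The order within Visit 2 rests on the numbering in Table 2. That the overseeing clinicians are among those at Visit 2 is likely but not stated, because Table 2 refers only to the clinical team. If they do not attend, no scheduled point collects the feedback that Section 3 expects of them. If they do, the only scheduled point follows the presentation.

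**The case against.** The strongest reply is that this order is the design. Section 4 sets up Part 2 so that clinicians can evaluate user, bench and motion-capture data. The safety features described in Section 1.2 are mechanical, electrical and software stops, which mannequin tasks may reveal only in part. On this view outcome 2 is an informed appraisal, and the presentation supplies what is being appraised. That stands: the presentation should stay, and its place before the discussion is not a fault. It does not answer the narrower point that no independent opinion is recorded before it.

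A reader might infer that the arrangement biases feedback in the device's favour. The documents do not show this. Visit 2 also brings back user results, and users are themselves asked about safety concerns, so the presentation could raise concerns as easily as settle them. Appendix 5 also asks directly for problems and improvements.

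A reader might also infer that nothing survives from Visit 1. That is too strong given the audio, the mannequin video and the Appendix 2 comments. An uncontrolled movement would be recorded on the day, so secondary outcome 1 is unaffected.

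It is also fair to say that sponsor personnel attend every device evaluation session (Section 4), so a Visit 1 form would not remove their presence. Individual written answers would still fix each clinician's view before the presentation and group discussion.

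**Conclusion.** The point holds as a gap in the schedule, and the remedy is a cheap improvement. Secondary outcome 2 has one scheduled collection point, expected 2-4 weeks after testing and listed after the sponsor's presentation, in a discussion that includes sponsor staff. No clinician opinion on the safety controls is scheduled to be recorded independently before then. The report could not distinguish observation at Visit 1 from conclusions reached after the presentation and discussion.

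The consequence is modest. This is a descriptive study of three to six users operating the device on a mannequin, and no error rate, sample size or numerical threshold is involved. What is at risk is the interpretability of one qualitative safety outcome that feeds a subjective feasibility judgement. The size and direction of any bias cannot be determined from the documents.

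The conclusion assumes that Table 2's numbering is the order of events and that Appendix 5 is not completed before the presentation. The documents do not settle the second assumption, and the plan should state it either way.

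**What to change.** 1. In Table 3, add Visit 1 to the clinician feedback row. Each clinician who oversaw testing answers Appendix 5 questions 2, 3 and 8 individually and in writing at the end of that visit.
2. At Visit 2, keep the presentation and the discussion as planned, but have each attending clinician answer Appendix 5 individually and in writing before the joint discussion. Clinicians who were not at Visit 1 answer the safety items before the presentation, as far as they can.
3. State in Section 4 when and how Appendix 5 is completed.
4. Report the Visit 1 and Visit 2 answers separately.

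The cost is a few minutes of writing per clinician (an assumption; the documents give no figure) and a little more descriptive reporting. No new staff or extra visit is needed. The survey period at the end of Visit 1, 30-60 minutes in Table 1, is a possible slot.
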